2.9 Exclusion Criteria

Participants are excluded from the study if any of the following criteria apply:

1. CST of $> 325 \mu\text{m}$
 - a. Fluid in the central subfield is allowed so long as CST is $\leq 325 \mu\text{m}$ and there is a normal foveal contour as determined by the Central Reading Center
2. Any prior focal or grid laser photocoagulation or any prior PRP in the study eye as it pertains to treatment of DME or DR (peripheral retinal hole treated with laser is allowed)
3. Eyes with DRSS score 61 with fibrous proliferations at disc or fibrous proliferations elsewhere
 - a. DRSS score 61B with NVE only is allowed. Any sign of fibrosis proliferation is exclusionary
4. Any prior systemic anti-VEGF treatment or IVT anti-VEGF treatment in the study eye
5. Any prior intraocular steroid injection in the study eye, inclusive of Iluvien® and Retisert®
 - a. History of Ozurdex® and triamcinolone use prior to 12 months before study enrollment is allowed
6. Current ASNV, vitreous hemorrhage, or tractional retinal detachment visible at the screening assessments in the study eye
7. Uncontrolled glaucoma or ocular hypertension in the study eye defined as an IOP $> 25 \text{ mmHg}$ regardless of concomitant treatment with IOP-lowering medications
8. Hypertension defined as systolic $> 180 \text{ mmHg}$ or $> 160 \text{ mmHg}$ on 2 consecutive measurements (during the same visit) or diastolic $> 100 \text{ mmHg}$
9. Screening HbA1c blood test $> 12.0\%$
10. Renal failure (stage 4 or end-stage), dialysis, or history of renal transplant
11. History of other disease, metabolic dysfunction, physical examination finding, or clinical laboratory finding giving reasonable suspicion of a disease or condition that contraindicates the use of an investigational drug or that might affect interpretation of the results of the study or render the participant at high risk for treatment complications
12. Initiation of intensive insulin treatment (a pump or multiple daily injections) within 4 months prior to randomization or plans to do so in the next 4 months
13. Epiretinal membrane, posterior hyaloidal traction, and/or vitreomacular traction in the study eye as determined to be significant by the Investigator
14. Previous pars plana vitrectomy in the study eye

15. Any intraocular surgery in the study eye within 90 days (3 months) prior to study enrollment
16. YAG laser treatment in the study eye within 90 days prior to study enrollment

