2.20 Statistical Considerations

2.20.1 *Statistical Hypotheses / Sample Size Determination*

This study is designed to evaluate the superiority of two doses of OTT166 (5 mg/day and 10 mg/day) compared to vehicle control for the treatment of DR. For each dose within each endpoint, the null hypothesis is that there is no difference between OTT166 and vehicle control or the difference is in the direction of inferiority of OTT166, and the alternative hypothesis is that there is a difference between OTT166 and vehicle control in the direction of superiority of OTT166. The vehicle control groups will be combined for all statistical analyses. No multiplicity adjustment is planned for this study.

The study will enroll approximately 210 participants randomized as described in [Section 2.14.3](#), 70 participants per group into each treatment arm and 35 participants per group into each matching vehicle control group and allowing for around 5% study attrition, aiming for at least 66 participants per treatment group and combined vehicle control group.

For the primary endpoint of improvement by at least 2 steps from BL on the DRSS at Week 24, completing 66 participants per group (active treatment BID, active treatment QID, combined vehicle control) through Week 24 will yield at least 90% power to demonstrate that the active treatment is superior to vehicle control using a 1-sided alpha of 0.05, provided that the true treatment effect (active treatment efficacy rate minus vehicle control efficacy rate) is at least 0.20 and the vehicle control efficacy rate is at most 0.06.

The sample size calculation was computed in nQuery 8.7 using a Chi square test for two proportions (continuity corrected).

2.20.2 *Outcome Measures*

The primary safety outcome measure of the study will be the proportion of participants who develop TEAEs through Week 24.

The primary efficacy outcome measure of the study will be the proportion of participants who have improved by ≥ 2 steps from baseline at Week 24 as determined by central reading center assessment using DRSS.

The secondary outcome measures are as follows:

- Proportion of participants developing worse than mild PDR (DRSS 65 and above) at Week 24
- Proportion of participants who develop ASNV at Week 24
- Time to development of PDR worse than mild (DRSS 65 and above)
- Proportion of participants who develop CI-DME at Week 24
- Time to development of CI-DME

- Proportion of participants developing VTC at Week 24

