Per-Protocol Set (PPS)	All ITT participants without any major protocol deviations that could impact the primary endpoint.
Safety Analysis Set (SS)	All participants who receive at least one dose of study drug. Participants will be included into the analysis based on treatment actually received, regardless of the treatment randomized.

The ITT Analysis Set will be used for all efficacy and BL analyses except participant disposition which will be shown for the ITT Analysis Set and for the Safety Analysis Set if the two analysis sets differ. All randomized participants are expected to be dosed and any exceptions will be described in the CSR. The PP set will be determined prior to database lock and will be used as supplementary analyses of the primary endpoint. All safety analyses will be based on the Safety Analysis Set (SS).

2.21 *Statistical Analyses*

2.21.1 *General Considerations*

Statistical analyses will include tabulations of summary data, inferential analyses, by participant listings, and figures.

All statistical tests will be one-sided and will be performed at the 5% level of significance, unless otherwise stated. The vehicle control group will be combined for all efficacy analyses, and two-sided 90% confidence intervals will be presented. Frequency counts (n and percentages) will be made for each qualitative variable. Descriptive statistics (n, mean, standard deviation [SD], median, minimum, and maximum) will be calculated for each quantitative variable, unless otherwise stated. All data will be summarized by treatment group. All safety summaries and analyses will be based upon the Safety Analysis Set by treatment group (i.e., vehicle control doses (5% BID, 5% QID), vehicle control combined, active OTT166 doses (5% BID, 5% QID), and OTT166 combined).

The BL value for analysis and reporting will be based on the last (non-missing) measurement before dosing on Day 1. If any safety measurements are repeated after dosing on Day 1, then the last (non-missing) value of any repeated measurements will be used in the descriptive statistics and in the calculation of changes from BL.

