### Secondary Efficacy Analysis:

#### *Secondary endpoints involving a proportion:*

Missing data for the secondary endpoints involving a proportion will be imputed using the same approach as described for the primary efficacy analysis (ICE handling and missing data imputation).

MAR imputation for the secondary endpoints involving a proportion will be generated based on a regression model with covariates for treatment group and the randomization stratification variable. Where appropriate, the dichotomous variable will be derived based on the imputed data.

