#### 4.10.1.4 Examination of Subgroups

The uniformity of the treatment effect for the primary efficacy variable will be examined for the following subgroups:

- Age (<65 years, ≥65 years)
- Gender (Male, Female)
- Race (White, Black or African American, Asian, Other)
- Ethnicity (Hispanic, Not Hispanic)
- BMI (Normal [ $<25 \text{ kg/m}^2$ ], Overweight [ $\geq 25$  to  $<30 \text{ kg/m}^2$ ], Obese [ $\geq 30 \text{ kg/m}^2$ ])
- HbA1C ( $\leq 7\%$ ,  $>7\%$ )
- Diagnosis of systemic hypertension (Y/N)
- Duration of Diabetes (<median, ≥median)
- Randomization strata (Screening DRSS:47 or 53 or 61B)
- Presence of fluid in the central subfield at Baseline (Y/N)

A forest plot with overall treatment effect included at the top will be provided.

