### 4.10.3 Secondary Efficacy Analysis

The secondary outcome measures are described in [Section 3.2.3](#). All secondary endpoints analyses will be performed on the Intention-to-Treat Analysis Set. The following secondary endpoint analyses will be repeated on the PPS:

- Proportion of participants who develop ASNV determined by the investigator at Week 24.
- Proportion of participants who develop CI-DME at Week 24.
- Change in DRSS steps is defined as DR worsening or improving by 1, 2, or  $\geq 3$  steps.
- Proportion of participants with mild PDR (DRSS score 61B) at baseline who regress to NPDR (DRSS score  $\leq 53$ ) by Week 24
- Mean and median change in BCVA (ETDRS letters) from baseline to Week 24.
- Lines gained/lost in BCVA ( $\pm 5, 10, \text{ and } 15$  ETDRS letters) at Week 24.
- Mean and median change in CST from baseline to Week 24.
- Proportion of participants who met the objective rescue criteria as defined in protocol section 2.14.9.
- Time to meet the objective rescue therapy criteria.
- Proportion of participants who develop VTC at Week 24

Continuous variable and changes from baseline will be summarized at each visit by treatment using descriptive statistics. Categorical variables will be summarized at each visit by treatment using frequencies and percentages.

The secondary endpoints involving proportions of participants will be analyzed using the same approach (MH test) as described for the primary efficacy analysis and based on the ITT Analysis set.

The categorical secondary endpoints will be compared using a proportional odds model with covariates for treatment group and the randomization stratification factor. If the assumption of proportional odds is rejected, a different analysis approach, such as a rank-based ANCOVA, will be

considered. The rank-based ANCOVA will be a two-sided test and a two-sided p-value will be presented.

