The time to event secondary endpoints will be defined as time to first development of an event and will be estimated based on the Kaplan-Meier method, along with a 90% confidence interval. Analyses will be based on observed data, where participants who receive rescue medication will be censored at the start of rescue medication. A stratified log-rank test adjusting for the randomization stratification factor will be performed, to compare the combined vehicle control with each treatment group. Additionally, a stratified Cox proportional hazards model adjusting for the randomization stratification factor will be employed to estimate the hazards ratio between the combined vehicle control and each treatment group.

Continuous secondary endpoints involving change from BL to Week 24 will be analyzed using an analysis of covariance (ANCOVA) model with BL measurement of the variable as a covariate and treatment group and the randomization stratification factor as fixed factors. As a sensitivity analysis of the continuous secondary endpoints involving change from BL to Week 24, a rank-based ANCOVA model will be employed. The pair-wise comparisons of each OTT166 dose group versus combined vehicle control will be done in the ANCOVA model. Two-sided 90% confidence intervals for the difference of each OTT166 dose group minus combined vehicle control will be calculated.

The specific reasons for meeting rescue criteria as described in protocol section 2.14.9 will also be summarized using number and percentage by treatment group.

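### The CI-DME proportion is analysed and imputed by DRSS stratum alone, although baseline CST and central fluid affect its risk by definition; the likely loss of precision is small

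*Protocol*

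**What the plan says.** - **Entry.** Protocol 2.9, exclusion 1a: "Fluid in the central subfield is allowed so long as CST is" no more than 325 µm and the reading center finds a normal foveal contour. Randomization (Protocol 2.14.3) is stratified by DRSS level only.
- **Event.** Protocol 2.16.10 counts CI-DME if fluid is present in the central subfield of an eye with none at baseline, or if CST exceeds 325 µm. CI-DME is also one limb of VTC (Protocol 2.16.9).
- **Proportions.** SAP 4.10.3: "The secondary endpoints involving proportions of participants will be analyzed using the same approach (MH test) as described for the primary efficacy analysis", so the strata are DRSS levels.
- **Imputation of proportions.** SAP 4.10.1.2 specifies a "regression model with covariates for treatment group and the randomization stratification variable".
- **Time to event.** SAP 4.10.3: "A stratified log-rank test adjusting for the randomization stratification factor will be performed". The Cox model is stratified in the same way.
- **Continuous CST.** Baseline CST is a covariate in the ANCOVA (SAP 4.10.3) and in the imputation model (SAP 4.10.1.2).
- **Other uses.** Baseline central fluid is a subgroup factor for the primary DRSS endpoint only (SAP 4.10.1.4). Baseline CST and fluid are also tabulated by arm (SAP 4.5).

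**The concern.** The entry ceiling and one event threshold are the same number on the same variable. An eye entering at 320 µm crosses the line with a rise of just over 5 µm; an eye entering at 250 µm needs just over 75 µm. If baseline fluid is read as central-subfield fluid, an eye that has it can become CI-DME only through CST. DRSS level measures neither feature.

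The SAP is also uneven. A missing Week 24 OCT is imputed with baseline CST for the CST endpoint, but the model named for the CI-DME proportion omits it, although CI-DME is partly a cut of that same Week 24 CST. Imputation may reach beyond the roughly 5% attrition allowed for: proportions inherit the primary intercurrent-event rules, and these replace data after premature discontinuation of study drug. Missing-at-random is easier to defend when the model includes pre-dose variables tied to the outcome.

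At stake is precision for a named secondary objective (CI-DME) and, in part, for a second (VTC), with about 66 to 70 participants per comparison group and no power stated for either.

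**Working it through.** **1. The plan's own figure.** Protocol 2.20.1 claims at least 90% power with 66 completers per group for the primary DRSS endpoint, if the difference "is at least 0.20 and the vehicle control efficacy rate is at most 0.06". That means 0.26 against 0.06, one-sided α 0.05, continuity-corrected chi-square.

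- Uncorrected: n = [1.645√(2×0.16×0.84) + 1.282√(0.26×0.74 + 0.06×0.94)]² / 0.20² = (0.853 + 0.639)² / 0.04 = 55.7, so 56.
- Corrected: (55.7/4) × [1 + √(1 + 4/(55.7×0.20))]² = 13.925 × 2.166² = 65.3, so 66. Power at 66 is 0.903.
- Attrition: 66/0.95 = 69.5, so 70.

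The figure reproduces and this point does not touch it. The documents contain no corresponding figure for CI-DME, so every input below is an assumption.

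**2. What adjustment can gain in principle.** If a baseline factor explains a fraction R² of the outcome variance, ideal adjustment multiplies the variance of the risk difference by (1 − R²). The SE falls by 1 − √(1 − R²).

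*Two-level factor* with prevalence f and risks p₀, p₁: R² = f(1−f)(p₁−p₀)² / [p(1−p)]. For f = 0.20 and 5% vs 25%, p = 0.09 and R² = 0.16×0.04/0.0819 = 0.078. The SE falls by 4.0% and the unadjusted variance is 1/(1−0.078) = 1.085 times larger. Over f = 10–50%, the SE falls by about 1% (5% vs 15%), 3–4% (5% vs 25%) or 7–10% (5% vs 40%).

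*Continuous baseline CST* (assumed mean 280, SD 25, truncated at 325), power to detect a halved risk with 66 per group. At a 10% rate, unadjusted power = Φ(0.05/√[(0.10×0.90 + 0.05×0.95)/66] − 1.645) = Φ(1.095 − 1.645) = 0.291.

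| Odds ratio per SD | 10% rate: SE cut | 10% rate: power | 20% rate: SE cut | 20% rate: power |
|---|---|---|---|---|
| 2 | 1.9% | 0.291→0.299 | 3.3% | 0.492→0.514 |
| 3 | 4.4% | 0.291→0.309 | 7.3% | 0.492→0.543 |
| 5 | 8.6% | 0.291→0.327 | 13.1% | 0.492→0.589 |
| 10 | 14.7% | 0.291→0.359 | 20.9% | 0.492→0.658 |

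These are ideal values. They ignore the cost of estimating coefficients from few events.

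**3. Simulated Week 24 CI-DME, adjusting for baseline CST and fluid** (assumed inputs).

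- Baseline CST about 275, SD 25–30, 25% with fluid, change SD 12–20, rates about 14–18% vs 6–8%, 66 per group: variance ratios 1.055 to 1.149. Power rises by 2.3 (0.484→0.507) to 7.3 points (0.458→0.531). The comparator was a DRSS-only standardised estimate, not MH.
- Mean CST 265–285, SD 22–27, change SD 15–30, new fluid independent of CST: variance ratios 1.03 to 1.14.
- SD 20–25, change SD 25–30, rates about 14–15% vs 8–9%: about +3 to +5 points over MH.
- A further set against MH with the Sato variance, 66 per group: variance ratios about 1.00 to 1.12, power −1 to +3 points.

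**4. Model stability.** The first set's rates imply 66×(0.14+0.06) = 13 to 66×(0.18+0.08) = 17 events per comparison. The model has five non-intercept parameters (treatment, two DRSS contrasts, CST, fluid). Ordinary logistic fits failed to converge in 10–20% of trials in the third set, where fewer than 10 events occurred in only about 5–6%. In the fourth set they failed or separated in about 14–70%, including many trials with 10 or more events. A rule based on a minimum of 10 events would therefore not protect the analysis.

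**5. Extra MH strata.** Adding CST tertiles changed power by −0.4 to +1.1 points; adding fluid changed it by −0.4 to −1.2. In a separate run (70 per group, 20% with fluid), DRSS-by-fluid strata moved the SE from 0.0451 to 0.0430 for 5% vs 30% risk. If fluid eyes were at lower risk (5% against 15% without fluid), it moved from 0.0495 to 0.0502. Cells are sparse: the 61B cap allows 0.20×70 = 14 per comparison group if balanced.

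**6. Time to CI-DME.** With 70 per group and 500 trials per scenario, adding both covariates to the DRSS-stratified Cox model raised power by 4.8 (0.356→0.404) to 7.8 points (0.320→0.398). Rejection under no effect was 5.6% without and 5.0% with the covariates. The Monte Carlo SE is √(0.05×0.95/500) = 1.0 point, so this shows no difference.

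**The case against.** The planned MH, log-rank and Cox analyses are stratified by the randomization factor, which is conventional and valid. These are secondary endpoints of a phase 2 trial, with no power claim and no multiplicity control. The continuous CST endpoint is already adjusted for baseline CST. The gain rests wholly on assumed inputs, can be nil, and comes with a model that has few events to support it. All of this stands, and it is why the planned analyses should be kept.

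SAP 4.10.1.2 also allows a dichotomous variable to be derived from imputed data where appropriate, which might be taken to bring in the CST imputation. It does not settle the matter: the model stated for the proportions has no baseline CST, and the fluid route cannot be derived from CST.

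A reader might infer that the objective-rescue endpoints need the same adjustment. The criteria in Protocol 2.14.9 do not support that. They are DRSS 65 or higher, ASNV, BCVA loss with new or increased fluid, and a CST rise of at least 75 µm from baseline with new or increased fluid. None uses 325 µm, and eyes with baseline fluid can qualify through an increase in it. For VTC and for PDR-or-CI-DME the case is weaker than for CI-DME, because other limbs also count, and neither was simulated.

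**Conclusion.** The point holds as a modest efficiency and consistency issue for CI-DME. Under the simulated inputs, leaving out baseline CST and fluid makes the variance about 0–15% larger, and adjustment changes power for the proportion by about −1 to +7 points. The larger ideal gains in the table need odds ratios of 5 to 10 per SD, which the documents neither support nor exclude. If baseline CST is only weakly prognostic, the gain may be negligible.

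Three stronger readings are not supported:

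- **That baseline CST and fluid largely decide who develops CI-DME.** The definition shows which route is open and how far the threshold is. It does not show how much of the risk this explains.
- **That the planned analysis is biased or its type I error inflated.** No calculation shows either. Richer imputation makes missing-at-random more plausible, but the present model has not been shown to give a wrong answer.
- **That adjustment leaves every estimand unchanged.** It does for a standardised risk difference. A Cox model with added covariates estimates a different, conditional hazard ratio.

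**What to change.** Before unmasking:

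1. In SAP 4.10.1.2, add baseline CST (continuous) and baseline central-subfield fluid (Y/N) to the imputation model for the CI-DME proportion and for the CI-DME limb of VTC.
2. In SAP 4.10.3, prespecify for CI-DME a risk difference adjusted for treatment, DRSS stratum, baseline CST and fluid, with a two-sided 90% CI. Use a method that does not fail with sparse events: a linear model with robust variance, or standardisation from a Firth-penalised logistic model. Report it beside the planned DRSS-stratified MH result.
3. For time to CI-DME, keep the stratified log-rank test and Cox model. Add a Cox model with the two covariates as a sensitivity analysis, and state that its hazard ratio is conditional.

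VTC and PDR-or-CI-DME may have the same adjustment as sensitivity analyses, with a smaller expected gain. Leave the objective-rescue endpoints as they are.

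The cost is SAP wording and a little programming; no new data are needed. The SAP still allows changes up to database lock (SAP 4.14). The downside is a model fitted to few events, which the choice of estimator and the retained MH result limit.

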2.10 Lifestyle Considerations

No study specific lifestyle restrictions are required. Participation in this study does not require modifications of lifestyle. Participants should follow their usual lifestyle, as part of their diabetes management plan.

2.11 Screen Failures

Screen failures are defined as participants who consent to participate in the clinical study but are not subsequently assigned to study intervention. A minimal set of screen failure information is required to ensure transparent reporting of screen failure participants to meet the Consolidated Standards of Reporting Trials (CONSORT) publishing requirements and to respond to queries from regulatory authorities. Minimal information includes demography, screen failure details, and eligibility criteria.

Individuals who do not meet the criteria for participation in this study (screen failure) may only be rescreened once. In any case, the Investigator must ensure that the repeated screening procedures do not expose the participant to an unjustifiable health risk. For re-screening, the participant must re-sign the ICF, even if it was not changed after the participant's previous screening.

Rescreened participants will be assigned a new participant number.

In case of abnormal or implausible results, which may be caused by intercurrent diseases, short-term treatable conditions, other temporary health disorders (eg, acute infection, laboratory changes, blood pressure outside defined range), or inappropriate circumstances (eg, inadequate rest when required, hemolysis), the investigator may decide to repeat the respective screening parameter(s) twice without rescreening (within 21 days).

2.12 Criteria for Temporarily Delaying Randomization / Study Intervention Administration

If a participant is otherwise eligible, the participant's study intervention may be postponed to allow acute intercurrent conditions to resolve. Under these circumstances, the screening period may be extended to 6 weeks upon discussion with the medical monitor.

